6.2.3.1 Maintaining Blinds

During treatment sessions, interventionists are asked not to refer to the participant by name and all quality assurance audio files are labeled only with the date of intervention, the session number, and the unique study identifier for the participant(s) involved. Because it is possible that the Research Assistant (RA) completing quality assurance may become aware of the identities of participants in the individual or group treatments, RA's who complete quality assurance will not take part in outcomes assessments (which will only be completed by Independent Evaluators through STRONG STAR).

Independent Evaluators will enter participant data from assessments directly into the secure STRONG STAR SQL Database using standard STRONG STAR operating procedures (see STRONG STAR Data Entry SOP, Appendix I).

** The PI and study physicians ([name], [name]) will sit in on weekly interdisciplinary staff meetings with study interventionists to discuss the progress of all study participants (both FORT-A and Treatment-As-Usual) during which participants will be discussed by case number only.

6.2.4 Followup Visits (see Figure 4)

Follow-up assessments will occur in the following intervals:

Visit	Measure	Assessment Window
Visit 2 (Baseline)	Psychosocial Assessment Pain Diary Functional Capacity Evaluation (FCE) Upload Actiwatch Provide and Train for MEMS Adverse Events Opioid/Medication Assessments (TLFB/SOWS/COMM/Concomitant Medications) MQS STRONG STAR Common Data Elements	≤ 2 weeks before treatment
Visit 14 (Post-Treatment)	Psychosocial Assessment Pain Diary FCE	≤ 2 weeks after treatment

	Upload Actiwatch Upload MEMS Adverse Events Opioid/Medication Assessment MQS STRONG STAR Common Data Elements	
Phone Assessments 1-11	Opioid/Med Assessment (TLFB) MQS	Monthly ± 1 week
Visit 15 (Six-Month Follow-Up)	Psychosocial Assessment Pain Diary FCE Upload Actiwatch Upload MEMS Adverse Events Opioid Assessment/Medication MQS STRONG STAR Common Data Elements	± 24 weeks after treatment ± 2 weeks

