AIM 2: Assess the efficacy of FORT-A for decreasing the rate of opioid recidivism (using any opioid for 3 or more days in any 30-day period) compared to standard PRC care in a sample of OEF/OIF/OND polymorbid CMP Veterans discharged off of opioid medication in VA care since the start of the OSI. Unlike the original FORT trial, this research will formally and prospectively track opioid medication use among polymorbid Veterans to sensitively detect changes in chronic opioid therapy attributable to FORT-A versus PRC treatment. FORT-A is expected to produce significant reductions in the rate of opioid recidivism by imparting numerous strategies to supplant opioid medication as a pain management strategy. FORT-A will avoid the stigma of “traditional” opioid abuse treatment and provide a pain management alternative to those who have been discharged from opioid medications as part of the OSI.

EXPLORATORY AIM 3: Based on the PI’s ongoing ESCAPE trial, this research team has identified psychological processes (helplessness, perceived burdensomeness) that likely play a mechanistic role in pain management among OEF/OIF/OND deployers. We will assess these constructs twice a week and analyze latent changes in FORT-A and PRC Veterans to ascertain their role as pain management mediators

Design and Outcomes

This study is a 1:1 block randomized clinical trial comparing the FORT-A program to treatment as usual for polytrauma OEF/OIF/OND Veterans with prior persistent opioid use and chronic musculoskeletal pain who are eligible for treatment through the STVHCS Polytrauma Rehabilitation Center. All participants will be offered Physical Therapy services before enrollment and will be enrolled after completing or denying Physical Therapy (up to 12 sessions as recommended by a PRC Physical Medicine & Rehabilitation Physician ([name], [name]). If they have already completed PRC Physical Therapy before study enrollment, they will not need to do so again. Also, if the Veteran qualifies but refuses PRC Physical Therapy, he or she will still be eligible to enroll in this study and will not be asked to complete PRC PT. Veterans randomized to PRC (treatment as usual) will then meet with PRC and other VA medical providers per usual standards of care (described below). Those

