The secondary outcome (addressing AIM2) for this research is rate of opioid medication recidivism. In consultation with study co-I and opioid dependence/misuse expert, [name], we decided to adopt a conservative definition of recidivism of use of any opioid for three days in any 30-day period. This definition was chosen (instead of a non-abstinent definition as described in McCabe et al., 2013) because this medical population may include veterans given short-term opioid therapy for a new injury or surgery and we did not want to count that as relapse or recidivism to opioid use. As was the case for disability, opioid use will be assessed through objective (MEMS caps) and subjective (timeline followback interview; TLFB) methods. Because some participants may shift patterns of other pain medication use as a result of discontinuing opioids, we will also complete TLFB for other pain medications and ask participants to use MEMS for their “most helpful” pain medication (if they are not taking an opioid med). All opioid medication use will be measured with MEMS and TLFB. We will also assess pain medication using the Medication Quantification Scale – III (MQS). The MQS was developed through the American Pain Society as a standardized method of quantifying pain medication use along dimensions of drug class, drug dose, and drug detriment (Harden et al., 2005). Both TLFB and MQS data will be gathered monthly (at all assessment intervals in person) and during monthly reminder phone calls. Previous studies have shown that Timeline Followback interviews demonstrate the best reliability and validity for long-term medication use (Kunoe et al., 2009), so TLFB was chosen as the focal secondary outcome measure for this research.

[figure not shown]

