Ongoing Assessments	MEMS/Actiwatch – Start at pre-treatment and end at 12-month f/u TLFB/MQS – Administered at pre- and post-treatment and every month after post-treatment.	
----------------------------	---	--

Study evaluators will maintain active logs for assessments identifying participants by unique ID # only and including date of evaluation, whether or not evaluation was in a study window, if PI approved out of window assessment (when outside of a window), whether an AE was identified in the assessment (e.g., suicidal ideation on the PHQ-9 item #9), and notes about assessment (see **Appendix F**). These logs will be monitored by the PI and coordinator weekly to ensure that assessments are completed on time. An example assessment log is as follows:

ID	Assessment	Assessment Domains	Assessment Date	Window? (Approved?)	Notes
10EX1	Pre-Treatment * within 2 wks before tx phase	Psychosocial	01/01/2001	Y	Treatment Phase Start 01/04/2001 End 01/25/2001 10EX1 forgot MEMS and Actiwatch at Post-Tx; PI approved out of window download; we can use data up to 01/25/2001 10EX1 sustained injury playing basketball on 07/20/2001; not cleared for FCE for 3 months; PI denied out of window assessment due to injury delay 10EX1 completed FCE on 01/24/2002 but not time for testing; r/s for when returns from vacation (01/24); PI approved out of window
		FCE	01/01/2001	Y	
		TLFB	01/01/2001	Y	
		MEMS	01/01/2001	Y	
		Actiwatch	01/01/2001	Y	
	Post-Treatment * within 2 wks after tx completed	Psychosocial	01/25/2001	Y	
		FCE	01/25/2001	Y	
		TLFB	01/25/2001	Y	
		MEMS	02/10/2001	N (Y)	
		Actiwatch	02/10/2001	N (Y)	
	6-Month *24 weeks ± 2 weeks after tx completed	Psychosocial	07/22/2001	Y	
		FCE	---	N (N)	
		TLFB	07/22/2001	Y	
		MEMS	07/22/2001	Y	
		Actiwatch	07/22/2001	Y	
	12-Month *50 weeks ± 2 weeks after tx completed	Psychosocial	02/07/2002	N (Y)	
FCE		01/24/2002	Y		
TLFB		02/07/2002	N (Y)		
MEMS		01/24/2002	Y		
Actiwatch		01/24/2002	Y		

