9.3 Definition of Populations

For this study, the per-protocol population will include all participants who completed all assessments and interventions with no major protocol deviations (as defined by Gupta, 2011). The primary analysis will be conducted on the Intent-to-Treat (ITT) population that will include all randomized participants who have completed baseline assessments. In the original trial, all FORT completers participated in all assessments, but approximately 20% of Treatment as Usual participants were lost to follow-up. Analysis of baseline data revealed that most missing data were missing at random.

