Medication Data will be adjudicated by the PI, the Research Coordinator, and [name] (an expert in trauma and addiction comorbidity). Timeline followback interview and MQS-III data will be discussed for each participant by the IE and the Coordinator within two business days of each assessment. If there are any noted problems with the TLFB data, then the assessment will be adjudicated by the above sub-committee within 2 days of review. MEMS cap data will be gathered for each participant's reported "most helpful" pain medication and any opioid medications they are prescribed by VA or other providers outside the VA system during the course of the study. MEMS data will be downloaded for each participant at each assessment follow-up visit. Upon download, the IE will scrutinize downloaded data to ensure that it falls within an expected range. If aberrant or missing data are noted, these will be adjudicated with the above sub-committee (and potentially discussed with the manufacturer if hardware or software problems are suspected) in a deidentified format.

The primary opioid endpoint will be the timeline followback (TLFB) interview. The TLFB represents the primary measure of opioid use because of its reliability and sensitivity as a daily measure of opioid use and its lack of perceived stigma compared to regular urine tox screen. A trained and masked IE will administer TLFB asking participants about any opioid medication use and use of other medications for pain. The TLFB Interview for this study was adapted from Sobell and Sobell (1992) as a semi-structured clinical interview asking the participant to use a blank calendar to describe the number of pain pills taken each day for 30 days. Instructions are provided to help the interviewer guide the participant in completing the recall as accurately as possible. This method has been reliably used in other trials of medication/opioid use and abuse (Kunoe et al., 2009).

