AIM 2: Assess the efficacy of FORT-A for decreasing the rate of opioid medication recidivism compared to standard PRC care in a sample of OEF/OIF/OND polymorbid LBP Veterans. To examine our primary hypothesis, we will compare the rate of opioid medication recidivism between the two groups monthly from baseline to 12-month follow-up. As noted above, 30-40% of TAU participants are expected to meet criteria for opioid recidivism (use of any opioid medication for 3 days or more in the last 30 days at each assessment). A statistically significant main effect will be interpreted as the groups exhibiting differential change in regards disability. Secondary analyses will be conducted using growth curve modeling (i.e., mixed effects hierarchical regression with polynomial change parameters to model differences in the trajectory of opioid use over time between the groups by time).

EXPLORATORY AIM 3: To examine the role of helplessness and perceived burdensomeness in predicting the trajectory of change over time, we will use latent

growth curve modeling. We will first model the trajectory of change in the two primary outcomes as a function of group (Aim 1 and Aim 2). We will then model the trajectories of helplessness and perceived burdensomeness as a function of group. Assuming both associations are observed (i.e., that group status is related to changes in the outcomes and the mediators), we will conduct hierarchical entry of group status and each mediator to examine if group status is still associated with outcome after adjusting for changes in the mediators. This will allow us to assess the role of the mediators in predicting the outcome and the proportion of change trajectory attributed to changes in these mediators.

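### Aim 2 counts opioid recidivism over any 30-day span, but a fixed 30-day TLFB at roughly monthly calls, analysed one interview at a time, cannot fully measure that definition

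*Combined protocol and SAP*

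**What the plan says.** The endpoint is worded in two ways.

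- Precis, Aim 2: "using any opioid for 3 or more days in any 30-day period". Section 3 agrees: "use of any opioid for three days in any 30-day period".
- Section 9.6, Aim 2 analysis: "use of any opioid medication for 3 days or more in the last 30 days at each assessment", with the arms compared monthly.

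The instrument and schedule are as follows.

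- Section 9.5.2 makes the TLFB the primary opioid measure. The participant uses a calendar to "describe the number of pain pills taken each day for 30 days".
- Section 5.4 gives the TLFB schedule: "Administered at pre- and post-treatment and every month after post-treatment". Section 6.2.4 sets the window for phone assessments 1 to 11: "Monthly ± 1 week".
- Section 9.2 rests Aim 2 power on 12 monthly data collection periods.

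No section extends the look-back to the previous completed interview, says what happens after a missed call, or joins successive interviews into one calendar. Section 9.6 offers a general missing-values analysis with LOCF and multiple imputation as examples, but no rule for TLFB days that were never asked about.

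**The concern.** A definition over any 30-day span needs an unbroken daily record. A fixed 30-day look-back gives one only if interviews are never more than 30 days apart, and the permitted window allows longer intervals.

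A second loss arises even without a gap. Use on the last two days of one interview's window and the first day of the next is three days within a 30-day span. Yet the interviews count two and one, so neither reaches three.

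At stake is whether the focal opioid measure captures the endpoint that Aim 2 states, and whether any shortfall is equal in the two arms.

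**Working it through.** **The plan's own figure.** Section 9.2 claims power 0.80 for 45% versus 22.5% with 65 per arm at α = 0.05 (two-sided assumed). For a single two-proportion test with pooled variance, the mean proportion is 0.3375:

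Φ[(0.225·√65 − 1.96·√(2·0.3375·0.6625)) / √(0.45·0.55 + 0.225·0.775)] = Φ[(1.814 − 1.311)/0.650] = Φ(0.775) = 0.781.

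The unpooled version gives 0.798. The stated figure is reproduced, and it assumes that every recidivist is detected.

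**Gaps allowed by the schedule** (interval minus 30-day look-back)

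- Calls exactly on time at 30.44-day months: about 0.4 day a month, or 4 to 5 days in 350.
- One call 7 days early, the next 7 days late: 30 + 14 = 44 days apart; 44 − 30 = 14 unasked.
- One missed call: 60 − 30 = 30 unasked; at worst about 60.9 + 14 − 30 ≈ 45.
- Baseline to post-treatment (Section 5.4 windows around three weeks of treatment): 14 + 21 + 14 = 49 days; 49 − 30 = 19 unasked.

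**Share of days unasked, by simulation.** Assumptions: 11 calls at 30.44-day spacing; timing uniform over the stated range; post-treatment TLFB 0 to 14 days after treatment; 6- and 12-month visits at 168 and 350 days (±14), always completed; calls missed independently.

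| Call timing | Calls missed | Days unasked |
|---|---|---|
| ±7 days | 0% | about 7% (25 of 350) |
| ±3 days | 0% | about 4% |
| ±7 days | 10% | about 14% |
| ±7 days | 20% | about 21% |
| ±7 days | 25% | about 24 to 25% |

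**Share of episodes detected** (±7 days; one block of consecutive use days; detected if at least three use days are covered by any interview, so split-window losses are not included)

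| Episode length | No calls missed | 20% missed |
|---|---|---|
| 3 days | 90% | 76% |
| 7 days | 95% | 81% |
| 14 days | over 99% | 87% |
| 30 days | 100% | 94% |

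**What differential loss could do, if unasked days were counted as no use** (a handling the plan does not state)

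- *Usual care misses 20% of calls, FORT-A none.* 3-day episodes: 0.45 × 0.758 = 0.341 versus 0.225 × 0.899 = 0.202. Power is about 0.43 (0.41 to 0.43 with simulation error). 14-day episodes: 0.45 × 0.867 = 0.390 versus 0.225 × 0.996 = 0.224, power about 0.54. 30-day episodes: 0.45 × 0.945 = 0.425 versus 0.225, power about 0.69.
- *Usual care misses 10%, FORT-A 30%.* 14-day episodes: 0.45 × 0.936 = 0.421 versus 0.225 × 0.792 = 0.178. The difference is 0.243, larger than the true 0.225.

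The bias can therefore run either way. The documents give neither miss rates nor episode lengths.

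**With each TLFB run back to the last completed one,** unasked days before the last contact fall to zero. Simulated detection is then 100% for every episode length tried and for miss rates of 0 to 30%, apart from recall error.

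**The case against.** **The analysis wording.** Section 9.6 sets what is tested. Its window is "in the last 30 days at each assessment", so a completed interview covers its window in full, call spacing loses nothing, and a missed call is missing data rather than a false negative. Hypothesis 3 in Section 1.1 also points to the 12-month assessment. This stands. It means that the under-count applies only to the Aim 2 and Section 3 definition. It does not settle the matter, because the analysis then measures something other than the stated endpoint.

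**The stronger reading.** A reader might infer that recidivism is under-counted more in usual care, biasing Aim 2 against FORT-A, since Section 9.3 reports that in the original trial "approximately 20% of Treatment as Usual participants were lost to follow-up". The documents do not support that. The figure is loss to follow-up in an earlier trial, not missed monthly calls. It sets usual-care participants against FORT completers, which are not like groups, and Section 9.3 adds that most of that missingness appeared random. The inference also needs unasked days to be scored as opioid-free, which no section says.

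**Other safeguards.** MEMS caps, the 12-month check of CPRS and the Texas prescription records (Section 9.5.2), and the late TLFB for participants lost to contact (Section 6.2.5) all help. But Hypothesis 4 makes MEMS and CPRS secondary measures, prescribing and dispensing records do not show days of use, and the late TLFB states no look-back. No rule lets any of them correct the TLFB endpoint.

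**Size.** Timing spread evenly over the full ±7 days is towards the unfavourable end. Unasked days are also not the same as missed recidivists, as the detection table shows.

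**Conclusion.** The point holds in limited form. The two definitions conflict, and the fixed 30-day TLFB on this schedule cannot fully measure the one in Aim 2 and Section 3. Gaps of 14 days between in-window calls and about 30 days after a missed call follow directly from the text. The 7%, 14% and 24% shares of unasked days rest on even spread over ±7 days and on assumed miss rates.

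The call window alone is a minor matter, affecting mainly short episodes; missed calls matter more. Under-counting of the Aim 2 definition is possible, and it would be differential if call completion differs by arm. Neither its occurrence nor its direction can be stated from the documents. The change is worth making because it is cheap and lets the trial measure the endpoint it names.

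**What to change.** - **Sections 6.2.4 and 9.5.2:** run each TLFB back to the date of the last completed TLFB instead of a fixed 30 days.
- **Section 9.6:** reconcile the two definitions. Derive recidivism over any 30-day span from the joined daily calendar with a rolling window. Treat days never asked about as missing, not opioid-free. Report days covered by arm.
- **Section 9.6, sensitivity analyses:** keep the monthly last-30-days measure, and name the use of MEMS and of CPRS with the Texas prescription records.

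The cost is a changed interview instruction, some programming and longer recall: about 60 days after one missed call and about 90 after two. Section 6.2.1 already uses a three-month TLFB at screening, so this is feasible. Recall length may then differ by arm if missed calls do, which is why the last-30-days measure should stay as a sensitivity analysis. The change cannot recover days after a participant's last contact.

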6.2.5 Completion/Final Evaluation

List each assessment to be performed at the participant's final visit.

Visit 16 (One-Year Follow-Up)	Psychosocial Assessment Pain Diary FCE Upload Actiwatch Upload MEMS Adverse Events Opioid/Medication Assessment (including CPRS and PAT) MQS STRONG STAR Common Data	± 50 weeks after treatment ± 2 weeks
----------------------------------	---	---

	Elements Exit Interview	
--	----------------------------	--

All participants will be asked to complete all final assessments, regardless of whether or not they complete the study. After completing the intervention, we will maintain monthly telephone contact with all participants to promote adherence to follow-up assessments and to give them an opportunity to report any adverse events they may have experienced since finishing the three-week intervention phase. This monthly contacts will also include monthly administration of the TLFB for pain medication and opioid medications and administration of the MQS. We will also use these monthly calls to identify and troubleshoot any potential problems with the Actiwatch or MEMS Caps.

Participants who were lost to contact at any point before the 12 month follow-up assessment will be contacted to complete the Missing Data Assessment, ODI, TLFB and Concomitant Meds Form. Participants will be mailed a letter explaining why they are being contacted, how long the phone interview will take, and what information we will collect. The letter will also include opt-out information. Within two weeks of the participants receiving this letter, we will contact participants to discuss whether they would like to participate. The Missing Data Assessment is a 4-item measure of global symptom improvement of pain, perception of satisfaction and burdensomeness of study treatments, and reason(s) for discontinuing study participation. This assessment will be used to assess missing data randomness and to categorize participants who discontinued study participation as a way to help impute missing data and improve future studies with these treatments in similar populations.

7. SAFETY ASSESSMENTS

Upon enrollment, all participants will be monitored for relevant risks through adverse events monitoring protocols (guided in part by the STRONG STAR AE SOP (see APPENDIX J). For this study, there is risk for adverse events related broadly to psychological distress, physical injury, and opioid withdrawal.

7.1 Specification of Safety Parameters

Section 7.3 of this protocol describes a number of formal assessment measures and related safety thresholds. Along with these formal assessment measures, we will also assess pain intensity ratings for each participant before and after each session of study-related Physical Therapy. The PI published a study of pain intensity ratings in functional restoration programs and noted that participants who reported pain on a 0-10 Numeric Rating Scale between 8-10/10 generally demonstrated worse outcomes after treatment. Thus, individuals reporting pain after PT sessions with pain ratings between 8-10/10 will be assessed for safety by [name] or a PRC PT/OT and discussed with the PI (using unique identification number).

